- **Adverse Events-** We will capture information on (1) changes in knee pain, swelling, and stiffness; (2) difficulty to bear weight on the surgical leg; (3) falls; (4) if subject has been hospitalized or disabled (> ½ day in bed or required to cut back on routine activities), and; (5) if subject had a TKR on the other knee. For information on falls we will ask subjects if they have had any falls using a 2-3 minute questionnaire developed at the Pittsburgh Pepper Center. One-week test-retest reliability (Kappa) was established as 0.89 in a sub-sample of 43 participants enrolled in a Pepper Center observational cohort study of older adults ([name] unpublished data). Falls will be defined as unintentionally coming to rest at a lower position. In this study serious adverse events (SAEs) are defined as hospitalization, death, or permanent disability. Adverse Events (AEs) are defined as exercise-related discomforts that remains for 3 days or longer (e.g., muscle and joint soreness/pain), minor injuries (e.g., strains, sprains), and non-injurious falls. Transient side effects are defined as complaints of increased pain, stiffness, or muscle weakness for periods of 2 days or shorter. We will compare the measures of harm such as adverse events and attrition by treatment interventions. If they differ between groups, they will be used as a covariate in the final outcome analysis.

We will also monitor attrition, adherence and co-interventions:

- **Attrition** is defined in this study as the number of patients dropping out of the study in each group.
- **Adherence** to intervention will be estimated by the proportion of sessions attended in each group and the proportion of patients missing each session. Adherence to the individualized outpatient exercise will be recorded by the physical therapist. Adherence to the group exercise classes will be obtained from reports generated by the community centers.
- **Co-interventions** will be queried during every assessment. Some subjects could decide to seek additional treatment options while enrolled in the study. We will ask about additional treatment sought (e.g., seeking specialized care), and participation in exercises besides the ones prescribed by the study. If the subject participated in additional exercises, we will record the frequency, duration, and type of the exercise and will analyze these data for their potential effect on the primary outcome.

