Hypothesis 2- A group of baseline biomedical and psychosocial measures will associate with treatment response.

Each subject will be classified as a responder or non-responder based on a minimum change score of 20% in BOTH the WOMAC-PF and the composite score of functional performance at 3 months, thus yielding a binary outcome. Baseline variables will be summarized separately for responders and non-responders. Unadjusted odds ratios will be estimated using univariate logistic regression. To consolidate potential predictors, we will test for collinearity among baseline variables that are associated with response. Baseline measures associated with response at the $p<0.15$ level in unadjusted models will be added to multivariable logistic regression models to assess predictors of treatment response. We will limit the number of predictors going into any one model to no more than one predictor per 10 responses (or 10 non-responses, whichever is less); if more variables are significant, the model will be limited to the most significant variables, after adjusting for those deemed a-priori to be clinically significant. We expect different predictors for each group. For example, patients with worse physical function and impairments (e.g., limited range of motion and muscle weakness) will do better with individual outpatient exercise whereas those with heightened psychosocial factors (e.g., anxiety and depressive symptoms) will respond better to group exercise in the community.^{48,70-72}

Exploratory Hypothesis- Adherence and co-interventions will be similar in all groups. The attrition rate and adverse events- mainly number of falls- will be lower in Groups 1 and 2 compared to Group 3.

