We will calculate dropout rates as proportions of subjects randomized and as a cumulative probability of remaining in the study using survival analysis techniques such as the product-limit estimator. This statistic can be estimated at various times following randomization and take into account when dropouts occur. Descriptive statistics will be used for reporting and evaluating implementation of the exercise protocols including the proportion in attendance for each session and the average number of sessions attended by group. The two intervention groups require the same number of exercise sessions (2 per week) for 3 months. To assess the impact of non-adherence, we could conduct a per-protocol analysis for the treatment effect but this would likely result in a biased estimate of the treatment effect due to selection bias of those who are more likely to adhere not representing a true random sample of trial participants. We propose to explore using instrumental variable methodology to estimate the efficacy for our interventions in the presence of non-adherence.⁹⁴ Instrumental variables have been mainly used in the econometrics⁹⁵ but have been proposed as a useful tool in estimating dose-response effects in psychological treatments where participants are expected to attend multiple sessions as part of the intervention protocol.⁹⁶ We propose to use the two-stage IV methods which can be easily implemented in Stata software using simple linear structural models for the effect of sessions attended on the primary outcome of function. We will also calculate the 6-month incidence (and 95% CI) of individual adverse events by organ system and relatedness to the study for each group. We will estimate the incidence of adverse events with specific focus on those deemed definitely, probably, or possibly related to interventions. For adverse events, clinical judgments will be considered more important than statistical testing.

Dropout and missing data analyses

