During our pilot study 100% of the patients completed the 2 month follow-up assessment;¹¹ however we are realistic and recognize that such retention rate is very optimistic for this study. Thus, in this study we estimate the attrition to be 10% at the 3 months follow-up. We also estimate the attrition to be 15% at 6 months, based on our pilot work and other studies with similar populations and timeframes. We will compare baseline characteristics between patients with and without the assessment at 3 and 6 months to assess potential biases in the complete case analysis. We will also try to obtain reasons for study drop out to assess the missing data mechanism (missing completely at random, missing at random, non-ignorable missingness). We will use several missing data methods for imputing data and re-analyze using intention to treat (as randomized) to assess the impact of missing data on our conclusions as recommended.⁹⁷ We

PRINCIPAL INVESTIGATOR (LAST, FIRST, MIDDLE): [name]

will first use multiple imputation (with M=10 imputations) which assumes the data are missing at random. Since the data could be missing not at random, we will use another approach of assigning the lowest observed scores for missing values differentially by treatment group (non-ignorable missingness). The approach assumes the missingness is directly related to the value of the missing data, i.e., the people who are missing data on function have worse function scores (did not come in for assessment because function was worse). Results of all approaches to missing data will be presented in the primary paper for our study. If our significance and interpretation of our treatment effect vary depending on the method of imputation, we will view any conclusions cautiously.

PATIENT POPULATION

Detailed reasoning of inclusion criteria is provided in Human Subjects.

Subjects will be included in the study if they underwent a unilateral TKR 2 to 4 months prior to study, are older than 60 years of age, experience functional limitation in daily activities (score in the WOMAC-PF of at least 9 points), *speak English sufficient to understand study instructions*, are willing to be randomized to one of the 3 treatment groups, and have medical clearance to participate in the study.

Subjects will be excluded if they:

- Have absolute or relative contraindications to exercise testing as established by the American College of Cardiology/American Heart Association;^{99,100}

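### The exploratory falls hypothesis is about a number of falls, but the plan names no count measure, no allowance for observed time and no method for comparing Groups 1 and 2 with Group 3

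*Combined protocol and SAP*

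**What the plan says.** The hypothesis, labelled exploratory in the Data Analysis section, reads: "The attrition rate and adverse events- mainly number of falls- will be lower in Groups 1 and 2 compared to Group 3". It concerns a count and gives a direction.

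The method for adverse events follows in the same section: "We will also calculate the 6-month incidence (and 95% CI) of individual adverse events by organ system and relatedness to the study for each group". Numerator, denominator and treatment of repeat events are not defined. The section adds that "For adverse events, clinical judgments will be considered more important than statistical testing".

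The Adverse Events paragraph, under Capturing Potential Harm of Interventions, has two further statements: "We will compare the measures of harm such as adverse events and attrition by treatment interventions" and "If they differ between groups, they will be used as a covariate in the final outcome analysis". Neither names a method. On data capture, the same paragraph says "we will ask subjects if they have had any falls using a 2-3 minute questionnaire". Table 1 places adverse events at the month 3 and 6 visits and at the month 1.5 and 4.5 calls.

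On follow-up, the dropout section expects 10% attrition at 3 months and says "We also estimate the attrition to be 15% at 6 months". The product-limit estimator is planned for dropout only.

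**The concern.** The hypothesis and the named method do not meet. A per-group incidence table with intervals describes each arm. It does not estimate how the number of falls in Groups 1 and 2 compares with that in Group 3. Because the measure is undefined, the analyst could choose it after seeing the data: proportion of fallers, falls per patient or falls per unit of time.

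The choice matters for two reasons. Falls can recur, and a proportion of fallers does not use the second and later falls. The hypothesis also predicts lower attrition in the exercise groups, so exercise patients would be watched for longer and have more time in which to report a fall. A measure that ignores observed time would then work against the very effect the plan hypothesises.

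Harms are one of the three stated foci in the Design Overview. Under the covariate rule quoted above, an undefined comparison of harms could also influence what enters the outcome model.

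**Working it through.** **Plan's own figure.** There is none to reproduce. The documents give no fall rate, effect size or power for falls.

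**Inputs from the documents.** 48 usual-care patients against 96 + 96 = 192 exercise patients (Sample Size); attrition 15% at 6 months (dropout section). Two-sided alpha of 0.05 is stated for the primary endpoint and assumed here.

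**Assumed inputs.** Fall counts are gamma-Poisson with dispersion k = 1.5. Usual-care means m are 0.2, 0.5 and 1.0 falls per 6 months, with rate ratios 0.5, 0.5 and 0.6. Dropout times are uniform over the 6 months.

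**Step 1: bias if incidence is the proportion with any fall among those randomised, with no true effect.**

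- Followed to month 6: F = 1 − (1 + km)^(−1/k). At m = 0.5, F = 1 − 1.75^(−2/3) = 0.3114.
- Dropouts, averaged over a uniform leaving time: D = 1 − [(1 + km)^(1 − 1/k) − 1] / [km(1 − 1/k)]. At m = 0.5, D = 1 − 0.2051/0.25 = 0.180.
- With attrition d, the observed proportion is (1 − d)F + dD.
- Exercise at d = 10%: 0.298. Usual care at d = 25%: 0.279. Ratio, exercise over usual care: 1.07.
- The same steps give 1.08 at m = 0.2 and 1.06 at m = 1.0.
- With 15% in every arm the ratio is 1.00.

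The 10% v 25% split averages 0.8 × 10 + 0.2 × 25 = 13%. Splits that keep 15% overall, under exponential fall and dropout times and a 6-month fall risk of 20% to 40%, give about 1.07 (12.5% v 25%) and 1.15 to 1.16 (10% v 35%).

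If incidence instead means total falls per patient randomised, the 10% v 25% split gives (1 − 0.10/2)/(1 − 0.25/2) = 0.95/0.875 = 1.09. That figure does not apply to the proportion of fallers.

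**Step 2: power, 48 v 192, 15% dropout in both, by simulation.** Ranges cover repeated runs.

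| Usual-care mean | Rate ratio | Proportion with any fall | Negative binomial with offset | Gain |
|---|---|---|---|---|
| 0.2 | 0.5 | 32% | 31% | none |
| 0.5 | 0.5 | 42–43% | 51–54% | about 10 points |
| 1.0 | 0.6 | 27–30% | 45–48% | about 18 points |

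Type I error was about 5% to 6%, so the gain does not come from a liberal test.

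**Step 3: hand check of the middle row.** Mean exposure is 1 − 0.15/2 = 0.925, so expected counts are 0.4625 and 0.23125. The variance of the log rate ratio is (1/0.4625 + 1.5)/48 + (1/0.23125 + 1.5)/192 = 0.0763 + 0.0303 = 0.1066, so SE = 0.3265. Power = Φ(0.693/0.3265 − 1.96) = Φ(0.16) = 56%, slightly above the simulated value.

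**Step 4: other dispersions.** With k from 0.5 to 2, rate ratio 0.5 and staged dropout (10% by month 3, 15% by month 6), an approximate calculation gives these changes from proportion to count model:

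- mean 0.2: 30–36% to 31–37%
- mean 0.4: 38–51% to 46–60%
- mean 0.6: 40–60% to 56–75%

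No scenario reaches 80%.

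**The case against.** The strongest reply is that this is an exploratory safety summary in a trial sized on WOMAC-PF, and that the plan openly ranks clinical judgment above testing for adverse events. Falls stay underpowered even under the better method, and the size of any gain rests on fall rates the documents do not give. All of that stands. It limits the weight of the point and is why the output should be an estimate with an interval.

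Some stronger readings are tempting but unsupported:

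- A reader might infer that no between-group comparison of harms is planned. The Adverse Events paragraph does plan one; what is missing is the method.
- A reader might infer that the plan counts a repeat faller once and an early leaver as fall-free. Incidence is not defined and could be a rate; that reading is one possibility.
- A reader might infer that recorded counts are being thrown away. The documents say only that patients are asked whether they have had any falls, and do not say that a number is stored.
- A reader might fear a spurious benefit of exercise. Under the attrition pattern the plan predicts, the bias runs the other way.

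None of these replies supplies a falls measure, a denominator or an effect measure for the stated contrast.

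**Conclusion.** The concern holds as a mismatch between a hypothesis about the number of falls and an undefined per-group incidence.

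The bias is conditional. It requires incidence to be read as a crude proportion and attrition to differ by arm. At 10% v 25% the null ratio is about 1.06 to 1.08, against exercise; at equal attrition there is none. The power gain is also conditional, from nothing at 0.2 falls per 6 months to about 18 points at 1.0, under the assumed dispersion of 1.5 and the rate ratios above.

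A count model makes better use of the data and answers the question as posed, but it does not make the trial adequately powered for falls. A reader might infer that the trial's main conclusion is at risk. The documents do not support that: the hypothesis is exploratory and the WOMAC-PF analysis is specified separately. The one link is the rule that harms differing between groups become covariates, and it gives a further reason to fix the falls measure in advance.

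**What to change.** In the adverse-event text of the Data Analysis section:

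- Define the outcome as the count of all falls per patient, injurious or not, from randomisation to month 6 or last contact.
- Analyse it with a negative binomial model with log(observed time) as offset.
- Report the rate ratio with 95% CI for Groups 1 and 2 combined v Group 3, and for each exercise arm v Group 3, labelled as exploratory estimates.
- Keep the 6-month incidence table as description, and state its numerator and denominator.
- Point the harms comparison in the Adverse Events paragraph to this analysis for falls.

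**Cost.** A few sentences of plan text, one short model and a data-capture check: the falls form at months 1.5, 3, 4.5 and 6 must store a number of falls and the last-contact date. If it records only yes or no, the form has to change.

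**Limit.** The offset corrects for unequal follow-up. It does not correct for dropout that is itself related to falling, and the report should say so.

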A Comparison of Treatment Methods for Patients Following
Total Knee Replacement

University of Pittsburgh

PCORI Award Number: CER – 1310-06994

Study Principal Investigator: [name]

Trial Registration: ClinicalTrials.gov Identifier NCT02237911

08/31/2014

A Comparison of Treatment Methods for Patients Following Total Knee Replacement.

Study Protocol

Design Overview - This comparative effectiveness study is designed to combine patient-centered research questions with rigorous research methods that minimize bias and balance internal and external validity. The pragmatic randomized clinical trial was selected to compare the treatments in ways in which they are delivered in routine clinical practice, so improving generalizability when informing what interventions work best. This will be a three group, single blind, pragmatic randomized clinical trial to answer the question: “In patients at later stages post TKR, given their personal characteristics, what are the comparative effectiveness and harms of the interventions available to them, among individual outpatient rehabilitative exercise, community-based group exercise classes, and usual medical care, especially with regard to physical function and activity?” This study focuses on: (1) outcomes of physical function and activity, both genuinely important to patients, (2) identifying predictors of functional recovery, and (3) potential harms of comparators. The design is depicted in the Figure above. In short, patients post-TKR will be informed about the study by their health care provider or by public announcement. Screening for eligibility will be done in two phases; over the telephone using a questionnaire, and in-person history and physical exam. Following pre-intervention evaluation, subjects will be randomized to one of the 3 groups:

1) clinic-based individual outpatient rehabilitative exercise; 2) community-based group exercise classes; or 3) usual medical care. The usual medical care group will continue their usual care whereas the other two groups will exercise during 12 weeks.

Endpoint measures will be assessed prior to and after intervention (3 months), and 6 months after randomization. After the 6 months follow-up, subjects in the usual medical care group will be randomized to either clinic-based individual outpatient rehabilitation exercise or community-based group exercise.

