- **Knee Impairments** – We hypothesize that patients with increased knee pain, decreased knee range of motion, and lower extremity muscle strength who participated in the outpatient rehabilitation will be able to improve physical function whereas the ones who participated in the community-based group exercise classes will not. Knee pain in the surgical and non-surgical knee will also be measured using an 11-point pain scale. Knee range of motion will be measured by a standard goniometer. We will measure the strength of the muscle groups that have been related to the outcome of TKR^{45,79} including knee extension strength and hip abduction strength measured using an isokinetic dynamometer (Biodex System 4 Pro, Shirley, NY) as we described before.⁴⁵

Capturing Potential Harm of Interventions- Growing evidence suggests that regular physical activity does not have deleterious effects on the survival of the prosthesis.^{80,81} The exercises we propose are not expected to cause any harm because they exert relatively low forces over the prosthesis.⁸²⁻⁸⁵ Regardless of the anticipated safety of the exercises, we will ascertain that interventions offer no harm by closely monitoring adverse events:

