Interventions – The choice of comparators was based on concerns that patients, physicians, physician assistants, physical therapists, and community groups have about the interventions available to them.

Clinic-based individual outpatient rehabilitative exercise: Results of studies on the effectiveness of outpatient rehabilitative exercise at later stage post TKR appear to support this practice.⁸⁻¹¹ Yet, as the evidence is limited, clinicians only prescribe this intervention to a relatively small number of patients. All patients we interviewed unanimously said that outpatient exercise at later stage post TKR was essential to allow them to function at higher levels. Discussions with physicians indicated that they would feel more comfortable increasing the utilization of exercise at later stage post TKR provided there was stronger evidence about its benefits and risks. The exercise program that we will use in this group has been shown

PRINCIPAL INVESTIGATOR (LAST, FIRST, MIDDLE): [name]

to be safe and feasible, and combines the best research evidence from ours and other groups of investigators.⁸⁻¹¹ Details of the program have been published (<http://www.ncbi.nlm.nih.gov/pubmed/20378678>). Subjects will participate in 12 supervised sessions of exercise followed by a home exercise program. The 12 sessions will be delivered during 3 months in the following schedule: 2 sessions per week during weeks 1-3; 1 session per week in weeks 4 to 7; and 1 session every 2 weeks after that (in week 9 and 11). The gradual weaning will ensure that subjects learn the exercises, which helps increase adherence with the home exercise program. The home program mimics common rehab practice. Patients are instructed to perform at home the same exercises as in the clinic starting after the 3rd week of supervised intervention in a way that they exercise twice a week (either supervised exercise in the clinic or at home) during the 3-month intervention phase. Each exercise session will last about 60 minutes. Treatment sessions will utilize a pragmatic approach and will include the following components:

- Warm-up with stretching of lower extremity muscles and range of motion exercises;
- Moderate to vigorous intensity strengthening exercises of the major lower extremity muscle groups (knee extensors, knee flexors, hip extensors and hip abductors);
- Moderate intensity aerobic training using a treadmill or exercise bicycle;

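### Adverse-event incidence is given a named window of 6 months only, although assigned exercise covers the first 12 weeks; incidence for months 0–3 and 3–6 should be added

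*Combined protocol and SAP*

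**What the plan says.** In the Combined protocol and SAP, the text under the Exploratory Hypothesis (Data Analysis) reads: "We will also calculate the 6-month incidence (and 95% CI) of individual adverse events", to be split by organ system and by relatedness within each arm. The next sentence adds: "We will estimate the incidence of adverse events with specific focus on those deemed definitely, probably, or possibly related to interventions". That sentence gives no window. The Adverse Events item under Capturing Potential Harm of Interventions plans a between-arm comparison, also without a window: "We will compare the measures of harm such as adverse events and attrition by treatment interventions".

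On exposure, the Design Overview says: "The usual medical care group will continue their usual care whereas the other two groups will exercise during 12 weeks". The Interventions section says of the clinic arm: "Subjects will participate in 12 supervised sessions of exercise followed by a home exercise program". It specifies twice-weekly exercise for the 3-month phase only, and group classes also run for 3 months. Usual-care patients are offered exercise only after their 6-month control period, so they have no assigned exercise in either half of the window.

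Table 1 schedules adverse-event collection at the month 3 and month 6 assessments and at the month 1.5 and month 4.5 calls.

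The harm aims are stated twice. The plan promises that "we will ascertain that interventions offer no harm by closely monitoring adverse events", and the Exploratory Hypothesis expects that attrition and adverse events, "mainly number of falls- will be lower in Groups 1 and 2 compared to Group 3".

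**The concern.** Half of the only named harm window falls after the assigned programme has ended. Harm caused by the sessions themselves, such as falls, strains or pain flares, would be expected mainly while patients attend them. Events at background frequency in months 3–6 then enter both arms and pull the 6-month ratio towards 1. If training also lowers fall risk later, which the plan's own hypothesis makes conceivable, the later benefit is netted against the earlier harm within one number.

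Benefit is treated differently. Patient-reported function has its primary comparison at 3 months and a separate contrast at 6 months for sustained effect. With no matching split for harms, a reader cannot set 3-month benefit against 3-month harm. Comparative harms are part of the trial's stated question, so this matters for interpretation even though the harm analysis is exploratory.

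**Working it through.** **Inputs from the documents.** Randomised numbers are 96, 96 and 48. With 10% attrition these give 96 × 0.9 = 86.4 and 48 × 0.9 = 43.2, which match the stated 86 and 43. The documents contain no adverse-event rate, effect size or power, so there is no plan figure for harm to reproduce.

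**Assumptions (mine).** Usual-care risk p is 5%, 10% or 20% in each 3-month half. The relative risk (RR) with exercise is 1.5, 2 or 3 in months 0–3, and 1.0 or 0.5 in months 3–6. Tests are two-sided at 0.05, with 48 usual-care v 96 exercise patients.

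**Formula.** 6-month risk = 1 − (1 − risk in months 0–3)(1 − risk in months 3–6).

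**Main case: p = 10%, RR 2 early, no effect later.**
- Usual care: 1 − 0.90 × 0.90 = 0.19.
- Exercise: 1 − 0.80 × 0.90 = 0.28.
- RR: 0.28/0.19 = 1.47, against 2.0 in months 0–3.
- Risk difference: 0.28 − 0.19 = 0.09, against 0.10. In general the early excess is multiplied by (1 − risk in months 3–6), here 0.10 × 0.90.

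**Power** = Φ((difference − 1.96 × SE₀)/SE₁), where SE₀ uses the pooled proportion and SE₁ the separate ones.
- Months 0–3: pooled 0.1667, SE₀ = 0.0659, SE₁ = 0.0595; (0.10 − 0.1291)/0.0595 = −0.489, so power is 31.2%.
- Months 0–6: pooled 0.25, SE₀ = 0.0765, SE₁ = 0.0728; (0.09 − 0.1500)/0.0728 = −0.824, so power is 20.5%.

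**Range, no effect in months 3–6.**

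| p per half | RR months 0–3 | 6-month risks | 6-month RR | Excess in points, 3 → 6 months | Power, 3 → 6 months |
|---|---|---|---|---|---|
| 5% | 2 | 9.75% v 14.5% | 1.49 | 5 → 4.75 | 14.9% → 11.0% |
| 10% | 1.5 | 19% v 23.5% | 1.24 | 5 → 4.5 | 11.6% → 8.3% |
| 10% | 2 | 19% v 28% | 1.47 | 10 → 9 | 31.2% → 20.5% |
| 10% | 3 | 19% v 37% | 1.95 | 20 → 18 | 79.9% → 60.4% |
| 20% | 2 | 36% v 52% | 1.44 | 20 → 16 | 68.4% → 44.1% |

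The excess relative risk is roughly halved, while the absolute excess keeps 80–95% of its size.

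**With later protection (RR 0.5 in months 3–6, p = 10%).** For RR 2 early, exercise risk is 1 − 0.80 × 0.95 = 0.24; 0.24/0.19 = 1.26, and the excess is 5 points. For RR 1.5 early, it is 1 − 0.85 × 0.95 = 0.1925; 0.1925/0.19 = 1.01.

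**What full cancellation needs.** The late exercise risk q must satisfy (1 − early exercise risk)(1 − q) = (1 − p)². At p = 10% and RR 1.5, q = 1 − 0.81/0.85 = 0.047, a late RR of 0.47 (0.43–0.49 over backgrounds of 20% to 5%). At RR 2, q = 1 − 0.81/0.80 = −0.0125, which is impossible.

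**Where relatedness protects.** Take exercise-related events only, clinic v group, with late risk 0–1%. Early risks of 5% v 10% with 1% late give 0.0595 v 0.109, RR 1.83. Early risks of 10% v 20% give 0.109 v 0.208, RR 1.91. With no late risk the RR stays 2.00. Dilution is then small.

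**The case against.** A reader might infer three stronger things that the documents do not support.

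- **That harms are summarised only over 6 months.** The plan also breaks incidence down by relatedness, focuses on related events and compares arms, the last two with no window stated. Six months is the only window named, not demonstrably the only one that will be used. For exercise-related discomforts the relatedness focus removes most of the dilution. It does much less for falls and serious events, and in usual care there is no assigned exercise to which an event could be related.
- **That a second half without sessions cancels an early excess.** It cannot. Cancellation needs a later protective effect, and with equal background risk in both halves no such effect can fully cancel an early RR of 2 or more. Nothing in the documents shows when harm or protection would occur.
- **That months 3–6 are unexposed.** The text does not say that participants stop exercising, and a home programme follows the clinic sessions. All that can be said is that the assigned 12 weeks are over.

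There are also fair arguments for leaving the plan alone. Per-group incidence with confidence intervals lets a reader see the absolute excess, which barely shrinks if there is no later effect. Six-month incidence by randomised arm is a legitimate summary of net harm in a pragmatic trial and captures later hospitalisation and disability. The analysis is exploratory, ranks clinical judgement above testing, and has low power in most scenarios in either window. The split could also be made at reporting, since the data will exist.

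These arguments stand against replacing the 6-month figure. They do not stand against adding the split in advance, because clinical judgement also needs to see when events occurred.

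**Conclusion.** The point holds as a minor improvement. The plan names one window for adverse-event incidence, and that window is about twice the length of the assigned programme. If an excess is confined to months 0–3, the 6-month ratio understates it: over assumed backgrounds of 5–20% per 3 months, a true RR of 2 reads as 1.44–1.49, with a loss of power. The absolute excess is little affected unless risk later falls below that of usual care.

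These sizes rest on assumed rates, on equal background risk in both halves, and on no dropout. They apply mainly to falls, serious adverse events and comparisons with usual care. The documents do not support saying that a harm would be hidden altogether, or that months 0–3 must become the main harm comparison. The primary efficacy conclusion does not depend on this point.

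**What to change.** In the adverse-event text under the Exploratory Hypothesis, keep the 6-month incidence and add that incidence with 95% CI of falls, adverse events and serious adverse events will also be given by randomised arm for months 0–3 (assigned programme) and months 3–6.

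Use person-time observed in each window as the denominator, so that patients lost to follow-up (10% expected at 3 months, 15% at 6 months) count only while observed. The contacts at months 1.5, 3, 4.5 and 6 are enough to place events on either side of month 3, and person-time can run to the last contact.

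State as well which window the unwindowed arm comparison and the related-events summary use.

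The cost is a few sentences and extra table columns, with no new data. The downside is fewer events and wider intervals in each window, which the retained 6-month figure partly offsets.
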